## **E. STUDY POPULATION**

The study population will consist of patients who are recommended to undergo an elective esophagectomy as determined by the surgeon's evaluation.

### **E.1. Inclusion Criteria**

- E.1.1 Undergoing an elective esophagectomy
- E.1.2 jejunal feeding tube placed at the time of surgery

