## B. BACKGROUND AND SIGNIFICANCE

Nutritional support is taking on an increasing focus in peri-operative surgical care. It is particularly important in esophageal resection, which is a high-risk operation in a patient population whose pre-operative condition may be reduced due to pre-operative chemo- and radio-therapy, as well as dysphagia from the cancer. Post-operatively, patients are routinely cleared to take nutrition by mouth once an esophagram is done post-operative day 7 and shows no abnormality.

Tube feeding should be at goal by day 7, but is discontinued once patients are discharged, as long as they are able to eat, i.e., do not have evidence of anastomotic leak or other serious complications. The amount patients are able to eat is frequently variable, and is not well recorded prior to or after discharge. There may be a dip in calories consumed, which if severe, will lead to readmission for

hydration, failure to thrive, or possibly the development of a post-operative complication.

Currently all patients are discharged with the jejunal feeding tube placed at the operation, just in case they are unable to eat post-operatively due to an unforeseen complication. Since many insurers and Medicare require patients to pay for tube feeding needed for less than three months (~\$800/month and up, plus the services of a home health nurse), we do not routinely require patients use the feeding tube once discharged.

For esophagectomy specifically, and upper gastro-intestinal surgery in general, there is very limited literature looking at this question. Small randomized studies have not shown a benefit to routine tube feeding, although the numbers were very small, ranging from 12 to 70 in each group. Furthermore, the duration of tube feeding averaged 14 days, and even in the groups being fed enterally, were not meeting caloric needs in the period studied.

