### **D. OUTCOME MEASURES**

The primary outcome measure for specific aim 1 will be the quality of life and patient satisfaction as measured by post-operative survey instruments.

Secondary Outcomes for specific aim 1:

- Complications following surgery (jejunal tube)
- Length of stay
- Costs

The primary outcome for specific aim 2 will be the occurrence of post-operative complications such as: atrial fibrillation, delirium, anastomotic leak, pneumonia within the 30-day post-operative time frame.

Secondary Outcomes for specific aim 2:

- Readmission rates and costs of care.

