### **E.2. Exclusion Criteria**

- E.2.1 Emergent procedure.
- E.2.2 Less than 18 years of age.
- E.2.3 Inability to provide informed consent or to complete testing or data collection.
- E.2.4 Unwillingness to be randomized.
- E.2.5 Tube feeding dependent on discharge.

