## **H. MEASUREMENT**

The assessment instruments that will be used for specific aim 1:

1. EORTC QLQ-C30, Quality of life in cancer patients

The complications assessment instruments that will be used for specific aim 2:

1. HUM00012731 data collected around the time of operation and post-operative visit.
2. Long-term data from HUM00012731

Patients will also be invited to enroll in the “Patient outcomes following esophagectomy for benign and malignant disease” HUM00012731, a study in which the PI ([name]) is also a co-investigator. To minimize patient burden, the baseline preoperative assessment and the evaluation for quality of life will be performed according to the protocol outlined in HUM00012731. Demographics and history forms HUM00012731 will only be administered once preoperatively. This data will then be shared to support the study aims of this protocol to minimize patient inconvenience. In the event, that a patient does not wish to be co-enrolled in HUM00012731, the attached forms (EORTC QLQ-C30 and Demographics and history forms HUM00012731) will be administered by the Thoracic Surgery Clinical Coordinator, who will be trained and added to the HUM000XXXXX study protocol, at the scheduled time points outlined in Section N.

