### **I.1 Demographics, Medical History, and Physical Examination**

#### **a. History**

- i. Age
- ii. Sex

- iii. Previous medical history
- iv. Prior thoracic procedures
- v. Primary diagnosis
- vi. Previous thoracic chemotherapy or radiation
- vii. Planned procedure
- viii. Comorbidities will be collected using the Charlson Comorbidity index collected at baseline

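### Section J leaves baseline quality of life and primary diagnosis, both collected, out of the 6-month comparison, although eligibility admits benign and malignant disease

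*Combined protocol and SAP*

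**What the plan says.** **Who can enter.** Section E defines the population by the operation: "The study population will consist of patients who are recommended to undergo an elective esophagectomy as determined by the surgeon's evaluation". E.1 asks for two things, "Undergoing an elective esophagectomy" and a jejunal feeding tube placed at surgery. The five exclusions in E.2 start with "Emergent procedure", and none of them concerns diagnosis. No passage says outright that benign cases will be enrolled, but nothing keeps them out. Section H also invites trial patients into a companion study whose title is "Patient outcomes following esophagectomy for benign and malignant disease" and whose data this trial will share.

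**What is measured.** Section D sets the Aim 1 primary outcome: "The primary outcome measure for specific aim 1 will be the quality of life and patient satisfaction as measured by post-operative survey instruments". The one instrument that Section H lists for Aim 1 is "EORTC QLQ-C30, Quality of life in cancer patients". It is completed before surgery (Section C, Section H.1(a) and Table 1 in Section N) and again up to 6 months. The baseline history in Section I.1 includes "Primary diagnosis".

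**What is done with it.** Section J plans a descriptive comparison of quality of life at 6 months, with no covariate, stratum or subgroup. Its randomisation paragraph describes one-to-one blocked allocation and names no stratification factor. The envelope procedure in Section F adds none.

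**The concern.** The plan foresees a mixed population and records the two baseline facts most obviously related to later quality of life, then uses neither. Benign and malignant patients can be expected to differ in their course to 6 months, since recurrence and further cancer treatment arise in only one of the groups. Quality of life before surgery is likewise a natural predictor of quality of life afterwards.

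An unadjusted summary leaves both sources of spread in the comparison. If the arms differ by chance in case mix or in baseline score, the reader has no planned way to separate that from an effect of tube feeding. The result is also harder to apply, because the background draws on cancer patients (it refers to "pre-operative chemo- and radio-therapy, as well as dysphagia from the cancer") while the estimate would come from a mixture of unknown proportions.

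**Working it through.** The plan gives no figure to reproduce. Section K has a placeholder for the sample size, and no standard deviation, effect size or benign share is stated. Everything below is illustration on stated assumptions.

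**Inputs**
- Patients per arm, n: 12, 35 and 70. Section B gives 12 to 70 per group for earlier trials; this trial's own number is not given.
- Benign share p: 15% assumed, with 5% and 30% as outer values.
- Quality-of-life gap d between benign and malignant patients: 15 points assumed, with 5 and 20 as outer values.
- Standard deviation of the 6-month score: 20 to 30 points assumed.

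**1. Chance shift from case mix (1 SD).** Formula: d × √(2p(1 − p)/n).
- n = 12: 15 × √(2 × 0.15 × 0.85/12) = 15 × 0.146 = 2.2 points
- n = 35: 15 × 0.085 = 1.3 points
- n = 70: 15 × 0.060 = 0.9 points

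At p = 5% and d = 5 the shift runs from 5 × 0.089 = 0.4 (n = 12) to 5 × 0.037 = 0.2 (n = 70). At p = 30% and d = 20 it runs from 20 × 0.187 = 3.7 to 20 × 0.077 = 1.5.

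**2. How that compares with ordinary sampling error.** The unadjusted standard error is SD × √(2/n). At SD 20 it is 20 × √(2/12) = 8.2 points with 12 per arm and 20 × √(2/70) = 3.4 with 70 per arm. The shifts in step 1 are already inside these standard errors; they are not added to them.

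**3. Share of variance due to diagnosis.** p(1 − p)d² = 0.15 × 0.85 × 225 = 28.7 points squared.
- SD 20: 28.7/400 = 7%; the standard error falls by 1 − √(1 − 0.072) = 4%
- SD 25: 28.7/625 = 5%; fall of 2%
- SD 30: 28.7/900 = 3%; fall of 2%

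At the outer values the share is 0.05 × 0.95 × 25 = 1.2, which is 0.3% of 400, and 0.30 × 0.70 × 400 = 84, which is 21% of 400.

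**4. Baseline score.** If the baseline and 6-month scores have correlation r, adjustment multiplies the standard error by about √(1 − r²). The documents give no r, so no figure is offered.

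**5. How often the arms would differ visibly.** With N patients in two equal arms and no stratification, the number of benign cases in one arm is hypergeometric. For N = 40 with 4 benign, only a 2–2 split avoids a difference of at least 10 percentage points, so the chance of such a difference is 1 − C(4,2)C(36,18)/C(40,20) = 0.605. The same calculation for benign shares of 10% and 20% gives 0.605 and 0.695 at N = 40, 0.263 and 0.402 at N = 80, and 0.032 and 0.111 at N = 200. Visible imbalance is likely in a small trial and uncommon in a large one.

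**6. Price of the extra term.** Each covariate uses one residual degree of freedom. With 12 per arm that is 1 of 22, or 4.5%, which is of the same order as the 3 to 7% of variance that diagnosis explains. With 70 per arm it is 1 of 138, or 0.7%.

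**The case against.** The strongest reply is that broad eligibility is a legitimate choice. Aims 1 and 2 concern recovery after esophagectomy without naming a disease, and most of Section B (oral intake after surgery, the jejunal tube, insurance cover) applies whatever the indication. Unstratified randomisation is valid, and chance imbalance in diagnosis is part of ordinary sampling error. The gain from adjusting for diagnosis is small on plausible values and could vanish at 12 per arm. The randomisation paragraph and Section L still hold open questions to the statistician, so the absence of strata may be unfinished text and not a decision. All of this stands.

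A reader might go further and infer that the QLQ-C30 is the wrong instrument for benign patients. The documents do not show this. The label in Section H describes the questionnaire; it says nothing about how it performs outside cancer, and the companion protocol that governs its use here is not among the documents. A reader might also infer that eligibility must be restricted to cancer, or that stratification is required. Neither follows. With 12 per arm and 15% benign, about 0.15 × 24 = 3.6 benign patients are expected in all, so incomplete blocks could leave the imbalance that stratification was meant to prevent.

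The reply does not explain why two baseline measurements that the trial already collects should stay out of its Aim 1 comparison.

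**Conclusion.** The point holds as one of precision and interpretation. The randomised comparison is not biased, and a reader who infers bias from the mixed population would be reading in more than the documents support.

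Under the central assumptions (15% benign, 15-point gap, SD 20 to 30), diagnosis accounts for about 3 to 7% of the variance and about 2 to 4% of the standard error. Over the outer values at SD 20 the variance share runs from under 1% to 21%. Baseline QLQ-C30 adds a gain that depends on a correlation the documents do not state. None of these figures can be fixed until the sponsor gives a sample size and an expected case mix. The instrument is used for Aim 1 only; the Aim 2 primary outcome, complications, does not depend on it.

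This is a worthwhile improvement at very low cost, not a threat to the trial's validity.

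**What to change.** In Section J, replace the descriptive Aim 1 comparison with the following:
- the between-group difference in QLQ-C30 score at 6 months, with a confidence interval, from a model with terms for randomised group, baseline value of the same score, and primary diagnosis (malignant or benign);
- the same estimate in patients with cancer, labelled as a supporting analysis;
- the number of benign and malignant patients in each arm.

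Stratifying the block lists by diagnosis is optional. It would mean two lists in place of one, and a small benign stratum may leave incomplete blocks.

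The cost is two baseline terms and no new data collection. The diagnosis term will be imprecise if benign cases are few, and in a very small trial it may buy little. Naming the terms before any outcome is seen prevents a choice of covariates after the event.

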### **E.2. Exclusion Criteria**

- E.2.1 Emergent procedure.
- E.2.2 Less than 18 years of age.
- E.2.3 Inability to provide informed consent or to complete testing or data collection.
- E.2.4 Unwillingness to be randomized.
- E.2.5 Tube feeding dependent on discharge.

## **F. RANDOMIZATION AND MASKING**

Randomization envelopes will be created at the start of the study. Each envelope will be opened prior to discharge or at POD#8 if patients are able to take adequate nutrition by mouth, to determine if post-operative tube feeding will be continued or not.

By consenting to the study, patients agree to continue tube feeding for at least 50% of caloric needs for 1 month post-operatively. Cross-over after randomization will be permitted for patient condition, although once randomized, patients will be analyzed by the original group.

- A copy of the signed research consent form must be included in the patient's hospital chart.

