### **C. STUDY SCHEMA**

Patients will be evaluated for surgery by the study surgeons. Patients scheduled to undergo an elective esophagectomy and who meet inclusion criteria (See Section E.1) will be approached for enrollment. Written informed consent will be obtained from all enrolled patients (see Appendix B). Pre-operative Quality of Life Survey will be obtained using the EORTC QLQ-C30 (see attached). Patients will then be randomly assigned to either routine post-operative tube feeding for 1 month, or usual practice, tube feeding to continue in the hospital until the patient is taking adequate nutrition by mouth at POD#8, or upon discharge. Since this study cannot be blinded, patients that cannot take nutrition by mouth at POD#8, or are tube feeding dependent on discharge will not be included in analysis.

Figure 1. Illustrates the study design

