## K. RECRUITMENT

An estimated sample size of XXXXX – insert from [name] evaluable\* patients will be enrolled over a period of 12-24 months.

\* Patients that meet inclusion criteria (see section E.1) and are not excluded from participation in the study by the exclusion criteria (see section E.2). If there are patients who drop out of the study or are loss to follow-up, they will be replaced to achieve a minimum sample size of XXXXX – insert from [name] evaluable patients for specific aims 1 and 2.

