## L. DISCUSSION OF POTENTIAL LIMITATIONS IN STUDY DESIGN

A potential pitfall is that patients who consent to the study in the preoperatively, may not continue to meet eligibility criteria prior to discharge or at POD#8 because they are not able to take adequate nutrition by mouth, thus excluding the patient from randomization and further participation in the trial.

Another potential pitfall is that patients who randomize to have their tube feeding discontinued at discharge may (due to patient condition) require tube feedings to be resumed to supplement nutritional needs. Cross-over after randomization will be permitted for patient condition, although once randomized, patients will be analyzed by the original group.

[name], how do we construct randomization schema and power analysis to account for these limitations?

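### Section C's analysis exclusions (oral intake at POD#8, tube dependence at discharge) can remove patients already randomised under Section F, against the plan's own rule to analyse randomised patients as assigned

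*Combined protocol and SAP*

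**What the plan says.** Five sections of the combined protocol and SAP bear on who enters the randomised comparison.

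- **Section F** opens the assignment on a test of oral intake at either of two times: "Each envelope will be opened prior to discharge or at POD#8 if patients are able to take adequate nutrition by mouth". The same section states that "once randomized, patients will be analyzed by the original group", and Section L repeats this.
- **Section C** places its test on the analysis, not on randomisation: "patients that cannot take nutrition by mouth at POD#8, or are tube feeding dependent on discharge will not be included in analysis".
- **Section E.2.5** excludes a patient who is "Tube feeding dependent on discharge". E.1 and E.2 contain no other criterion on feeding or intake.
- **Section L** says that consented patients may cease to be eligible "prior to discharge or at POD#8 because they are not able to take adequate nutrition by mouth, thus excluding the patient from randomization".
- **Section K** defines evaluable patients by E.1 and E.2 alone.

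Table 1 (Section N) has a starred inpatient eligibility re-check before randomisation, without a day or a criterion. Neither *adequate* nor *tube feeding dependent* is defined anywhere.

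**The concern.** An entry test that is complete before allocation shapes the trial population but leaves the comparison intact. The same test used to remove patients after allocation is different, and most of all when it depends on something that happened after allocation.

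Section F permits randomisation at POD#8, yet Sections C and E.2.5 look at status at discharge, which may be later. In that interval one arm is still being tube fed because it was assigned to be (Section F asks for at least 50% of caloric needs for 1 month) and the other is not. Being judged tube dependent at discharge can therefore depend on the assignment. It can also depend on outcome: Section B explains being able to eat as having no evidence of anastomotic leak or other serious complication, and leak is among the primary outcome events for Aim 2 in Section D. Dropping such patients could remove events from the analysis, and not necessarily equally in the two arms.

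**Working it through.** No figure in the plan is at issue, so the check sets the rules side by side and follows patients through them.

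| Section | Test | Time | Consequence |
|---|---|---|---|
| C | unable to take nutrition by mouth; or tube dependent | POD#8; discharge | not analysed |
| E.2.5 | tube dependent | discharge | excluded from trial |
| F | adequate oral nutrition | before discharge or POD#8 | envelope opened |
| L | inadequate oral nutrition | before discharge or POD#8 | not randomised |
| K | by reference to E.1 and E.2 | as E.2.5 | not counted as evaluable |

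**Route 1: the late recoverer.** Grade oral intake as none, partial or adequate at POD#8 and again at discharge. If intake never worsens there are six paths. Two terms need an assumption: *dependent* may mean no oral intake or inadequate oral intake at discharge, and Section F may accept adequacy at either time or only at POD#8. Counting the paths on which C, E.2.5 and F do not all agree gives:

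| *Dependent* means | F tested at | Paths in conflict |
|---|---|---|
| inadequate intake | either time | 1 of 6 |
| inadequate intake | POD#8 only | 2 of 6 |
| no intake | either time | 3 of 6 |
| no intake | POD#8 only | 4 of 6 |

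No combination removes the conflict. The one path in conflict under all four is none at POD#8, adequate at discharge: in under E.2.5, out under C. He is also in under F whenever either time counts, which is what F literally says. On that reading he is randomised before discharge and then dropped for his earlier POD#8 status.

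**Route 2: dependence arising after allocation.** This lies outside the six paths because status worsens.

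1. At POD#8 intake is adequate, so F opens the envelope.
2. By discharge the patient takes nothing by mouth. He is then dependent on either reading of the word, and C removes him from analysis. If intake falls only to partial, C removes him when *dependent* means inadequate intake and keeps him otherwise.
3. F and L require that he stay in his assigned group.

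Section L foresees a control patient who has to resume tube feeding, and keeps that patient in the original group. If tube feeding resumes shortly before discharge and the patient goes home dependent on it, C drops the patient. If it resumes shortly after discharge, L's rule applies. The same clinical event is thus handled in opposite ways on either side of the discharge date.

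These are counts of logical paths, not of patients. The documents give no distribution of intake at either time, and the sample size in Section K is still a placeholder.

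**The case against.** The strongest reply is that Section C loosely describes patients who are never randomised. Section L speaks of exclusion from randomisation and further participation, and Table 1 puts an eligibility re-check before randomisation. If that was the intent, nobody is lost after allocation. This is plausible, and it is why a change of wording is enough. But Section C's sentence speaks of analysis and follows the sentence on assignment. A discharge criterion also cannot be checked in advance for a patient randomised at POD#8 who is not yet going home.

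Second, on Route 1, POD#8 status precedes a randomisation done at discharge. Removing patients on a pre-randomisation characteristic, alike in both arms, costs precision and breadth but does not by itself bias the comparison. That stands. Route 1 is a contradiction and a loss of randomised patients; the risk of bias comes from Route 2.

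Third, a reader might infer that partial eaters are in under Sections C and E and out under F and L, so that the trial's population is itself in dispute. The documents do not establish this. The sentence in Section C before the exclusion, and item 4 of G.1, both continue in-hospital tube feeding until oral nutrition is adequate, and Section L treats inadequate intake as a failure of eligibility. If *dependent* means inadequate intake and F accepts either time, the sections agree on partial eaters. Section B does describe usual practice as stopping tube feeding in patients who are able to eat, so the other reading is open too. The point is conditional on definitions that the plan does not give.

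Nor do the documents show that an adequacy test would keep out the patients expected to benefit. Section B places the possible calorie dip after its account of stopping tube feeding at discharge in patients who can eat, so the dip may occur in patients judged adequate at that time.

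**Conclusion.** The point holds in this form. Section C's exclusion from analysis conflicts with randomisation under Section F and with the rule in F and L that randomised patients stay in their assigned group.

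The late recoverer is treated inconsistently on every reading tested, and is randomised then dropped if F accepts either time. Route 2 is the more serious, because the exclusion depends on post-allocation status in an unblinded trial whose arms differ in tube feeding at that moment. It requires only that some envelopes are opened at POD#8 ahead of discharge, which F allows. Neither the direction nor the size of any bias can be derived from the documents.

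The plan should be changed, but this is a correctable inconsistency and not proof that the comparison is invalid. Inconsistent handling of partial eaters remains a possibility that turns on the meaning of *adequate* and *tube feeding dependent*.

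**What to change.** 1. Apply the oral-intake and tube-dependence eligibility test once, immediately before the assignment is opened, at the starred re-check already in Table 1.
2. State in Section C that patients who fail this test are not randomised, and delete the test as an exclusion from analysis. Every randomised patient is then analysed in the original group, as F and L already require.
3. Reconcile Sections C, E.2.5, F, K and L to one criterion with one wording, so that eligibility and the count of evaluable patients do not depend on status that may arise after allocation. The sponsor must settle what *adequate* and *tube feeding dependent* mean; no cut-off or day is proposed here.

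The cost is protocol wording at an assessment that already exists. The downside is that some randomised patients who later become tube dependent stay in the analysis, which may slightly dilute the contrast between arms. Reporting the number of such patients by arm would let readers judge this.
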